culprit lesions.²² The combination of stenosis + atheroma burden + luminal area produced an odds ratio of 3.99 (95% CI: 1.74-9.13, p=0.001) for culprit plaque. The GLAGOV study showed that PCKS9 inhibition reduced the percent atheroma volume of coronary arteries over a 78 week treatment period.²³ With atheroma volume now established as a viable biomarker, vwMRI is the optimal test to monitor it and stenosis, both for ICAD and in other locations of the cerebrovasculature, such as the carotid arteries, cervical vertebral arteries, and aortic arch.

A.5. Impact

The result of this study will be a dataset that lays the foundation for a randomized controlled trial of Repatha in ICAD patients. The data collected in this study will allow us to optimize a future clinical trial designed to demonstrate a reduction in stroke risk, ultimately making more efficient and economical progress towards our ultimate research goal of preventing stroke with Repatha. While we are proposing future studies to reduce ICAD stroke risk, it should be noted that our study will also evaluate the potential for Repatha to decrease cerebrovasculature stenosis and plaque burden, which would be a compelling primary prevention indication.

B. Approach

B.1. Study Hypothesis

We hypothesize that inhibition of PCSK9 with Repatha in patients with moderate to severe intracranial atherosclerosis will reduce validated biomarkers of stroke risk (stenosis and percent atheroma volume). To answer our hypothesis, we propose a single arm study of Repatha in 150 patients with a prior history of ischemic stroke and ICAD causing at least 50% stenosis of a major intracranial artery in the Circle of Willis ("index artery").

B.2. Study Design

We will enroll 150 ICAD patients with a prior history of ischemic stroke. Patients will be enrolled at up to 8 medical centers in North America. All patients will receive Repatha for 78 weeks and will have an MRI before beginning study medication and a comparison MRI immediately after completing study medication.

B.3. Investigational Treatment

The investigational treatment is Repatha 140 mg administered subcutaneously with a single-dose pre-filled pen syringe every 2 weeks for a total of 39 treatments. Dose modification is not allowed.

B.3.a. Inclusion Criteria

- Adult patients, ≥ 18 years of age

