- History of ischemic stroke, defined as an episode of neurological dysfunction caused by focal cerebral, spinal, or retinal infarction (American Heart Association definition).
- Large vessel atherosclerosis of an intracranial artery in the circle of Willis with 50-99% stenosis by WASID criteria (percent stenosis = (1-[diameter stenosis/diameter normal]) x 100%) on MRA, CTA or DSA
 - Eligible arteries: vertebral (V4), basilar, PCA (P1, P2), MCA (M1, M2), tICA, ACA (A1)
- Current statin use or contraindication to statin
- Fasting LDL-C ≥ 70 mg/dL or LDL-C ≥ 60 mg/dL if lipoprotein (a) > 30 mg/dL; within a year of randomization and on the current statin medication/dose

B.3.b. Exclusion Criteria

- Gadolinium or PCSK9 inhibitor allergy
- Acute or chronic kidney disease with eGFR<30 ml/min/1.73m²
- Pacemaker or other MRI contraindications per American College of Radiology guidelines²⁴
- Inability to return for 78 week follow-up clinic visit and vwMRI

Pregnant at time of enrollment

B.4. Investigational New Drug Status

We will not require an IND. Repatha is indicated to reduce the risk of myocardial infarction, stroke, and coronary revascularization in adults with established cardiovascular disease; and as an adjunct to diet, alone or in combination with other lipid-lowering therapies (e.g., statins, ezetimibe), for treatment of adults with primary hyperlipidemia to reduce low-density lipoprotein cholesterol (LDL-C). Our patient population meets these criteria given 1) history of ischemic stroke and 2) presence of moderate to severe ICAD.

B.5. Patient Recruitment

Patients will be approached first by a member of their clinical care team in order to gain permission for a study member to approach to discuss the study in detail. Only co-investigators or study coordinators on this study will consent patients. Standard consenting procedures will be followed, including giving patients and family members adequate time to discuss the study with the study team and amongst themselves prior to consenting. A full, written, IRB- approved Informed Consent document will be provided to the patient (or representative) for signature after the patient or patient's representative has had time to read it and ask questions. A copy will be given to the patient for his/her records. Proxy consent by legally authorized representatives will be allowed in the case of post-stroke aphasia or other cognitive disability, in order to not bias study entry by stroke severity.

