We will fit a mixed effects linear regression model, specifically a LOESS smoothing curve, to change in stenosis/PAV and on-treatment LDL-C, HDL-C, and lipoprotein(a). We will also use a multivariable linear regression model with the outcome of the primary endpoints, adjusted for covariates that could be confounders such as age, gender, smoking, statin use/dose and relevant medical comorbidities. The primary endpoints will also be compared to an assumed value of 0% change in stenosis and PAV that would correspond to optimal medical management without a PCSK9 inhibitor. Although, some studies have suggested statin therapy can reduce carotid atherosclerosis, no such effect is known for ICAD. For this analysis, we will use linear mixed effects model to detect differences in the stenosis and PAV endpoints between patients taking Repatha or the presumed historical control values of 0% change. For the secondary endpoints, we will use logistic and linear regression depending on the nature of the variable and use the primary predictors of on-treatment LDL-C, HDL-C, and lipoprotein(a). For the exploratory endpoint of recurrent stroke, we will use the above mentioned methods as well as a Cox proportional hazards model for the endpoint of recurrent stroke with the observed rate in this study compared to controls matched according to degree to stenosis of the index artery. Due to differences in arterial structure and flow dynamics, there may be a more significant plaque reduction in certain intracranial vessels. We anticipate subgroup analyses, for example comparing change in stenosis or PAV in the middle cerebral artery versus the vertebral artery.

D.2. Power Analysis

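### With no minimum time from stroke to baseline MRI and a fixed 0% comparator, any non-drug lumen recovery in a recently symptomatic artery would be credited to Repatha; its size is unknown

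*Combined protocol and SAP*

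**What the plan says.** **Entry.** Section B.3.a asks for "History of ischemic stroke, defined as an episode of neurological dysfunction caused by focal cerebral, spinal, or retinal infarction". Neither the entry criteria nor the schedule in Figure 1 sets an interval between that stroke and the baseline scan, and the stroke need not lie in the territory of the stenosed artery. The only dated entry condition is the LDL-C value, "within a year of randomization and on the current statin medication/dose".

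**Design and imaging.** Section B.1: "we propose a single arm study of Repatha in 150 patients with a prior history of ischemic stroke". Section B.2 ties the scans to the drug and not to the stroke: patients "will have an MRI before beginning study medication and a comparison MRI immediately after completing study medication".

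**Comparator.** Section D.1: "The primary endpoints will also be compared to an assumed value of 0% change in stenosis and PAV", a value "that would correspond to optimal medical management without a PCSK9 inhibitor". For PAV, D.2 cites a coronary trial whose placebo arm rose 0.05%. D.1 adds that no statin effect is known for intracranial disease.

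**Adjustment.** The regression in D.1 is "adjusted for covariates that could be confounders such as age, gender, smoking, statin use/dose and relevant medical comorbidities". Time since stroke and culprit status are not named.

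**PAV.** Section C.1.a computes PAV from outer-wall area and lumen area, on the slice with the tightest stenosis.

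**The concern.** At the baseline scan the qualifying stroke may be days or years old. If part of the narrowing in a recently symptomatic artery is temporary, for example thrombus lying on plaque, the lumen could widen over 78 weeks whatever the patient takes. A concurrent control arm would show the same change and cancel it. A fixed 0% cannot.

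Both primary endpoints are exposed. Stenosis is a lumen measure. PAV falls arithmetically whenever the lumen grows inside an unchanged outer wall, even if the atheroma itself has not changed. Averaging over about four sites dilutes the effect in the all-artery analysis, and less so in the separate intracranial analysis.

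Section A.5 says the data are to lay the foundation for a randomised trial, so an inflated estimate of regression would carry into that trial's planning. If stroke date and culprit status are not recorded, nobody can show afterwards that the distortion was small.

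**Working it through.** **1. The plan's own figures.** Inputs from D.2: 150 patients, four sites each (600 arteries), SD 4 PAV points, two-sided 0.05, a 1-point reduction against 0.

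- Power with patients as the unit: Φ(1 × √150 / 4 − 1.96) = 86.5%, so the stated >80% reproduces.
- Detectable effect at 80% power: (1.960 + 0.842) × 4 / √n. This gives 0.915 at n = 150 and 0.457 at n = 600. The stated 0.51 needs n = (2.802 × 4 / 0.51)² ≈ 483, a design effect of 600/483 = 1.24, or an intra-class correlation of (1.24 − 1)/3 ≈ 0.08. The plan states no correlation; I use 483 because its own figure implies it.

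**2. From lumen recovery to PAV (all assumed).** Take a circular lumen and stenosis falling from 60% to 50% without drug effect. Lumen area, relative to normal, goes from 0.40² = 0.16 to 0.50² = 0.25, a gain of 0.09. Hold outer-wall area at 1.3 to 2 times normal lumen area. PAV = (outer wall − lumen) / outer wall, so it falls by 0.09/2 = 4.5 points to 0.09/1.3 = 6.9 points in an affected artery.

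**3. Dilution.** Let 10-30% of index arteries be affected, one of four sites per patient.

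- Low end: 0.10 × 4.5 / 4 = 0.11 points.
- High end: 0.30 × 6.9 / 4 = 0.52 points.

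**4. Chance of a false finding of regression when the drug does nothing.** Formula: Φ(m / (4/√n) − 1.96), where m is the mean drift.

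| Effective n | m = 0 | m = 0.11 | m = 0.52 |
|---|---|---|---|
| 483 (implied by 0.51) | 2.5% | 9% | 81% |
| 338 (30% lost: 0.7 × 483) | 2.5% | 7% | 67% |
| 105 (30% lost, sites fully correlated) | 2.5% | 5% | 26% |

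A mild case: 10% of patients with a 1-point PAV fall at one of four sites gives m = 0.10 × 1 / 4 = 0.025 and a chance of 3.4% at n = 483.

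**5. Stenosis.** The plan states no SD or detectable change for stenosis, so the same calculation cannot be made for that endpoint.

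**The case against.** The strongest reply is that the mechanism is not in the documents. Nothing there says that recently symptomatic intracranial lesions widen untreated, or by how much, and entry is open to remote and unrelated strokes, so the share of fresh culprit arteries is unknown. That stands. It limits the point to what the plan would do with such a change if it occurred.

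Four stronger readings are tempting, and the documents do not support them.

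- *That spontaneous resolution will be counted as drug effect.* Only the route is established, not that the change happens.
- *That the 0% value describes stable disease.* D.1 speaks of medical management without a PCSK9 inhibitor and says nothing about stability.
- *That a recanalising embolus adds to the problem.* Entry requires atherosclerosis, and Figure 1 has CTA or MRA reviewed to confirm it. An embolus would get in only through misclassification at screening.
- *That a 10-point fall in stenosis can be set against the 0.51% detectable effect.* That figure is for PAV.

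The plan also has partial protection. Medical history is taken at baseline, a physician reviews records for stroke (C.3.a), diffusion imaging is part of the scan (C.1.a), the covariate list is open-ended, and the LDL-C analysis gives some evidence that does not rest on 0%. None of this pre-specifies an adjustment or corrects the test against 0%.

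**Conclusion.** The structural gap holds: no stroke-to-scan interval, one arm, a fixed 0%, and no named term for time since stroke or culprit status. Any non-drug lumen recovery would be credited to Repatha in both endpoints.

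The size is unknown. The 9-81% range for a false finding on PAV rests on the assumed share, the assumed fall in stenosis, the lumen and wall geometry, one index artery in four sites, and the effective sample size implied by 0.51%. Heavier within-patient correlation or dropout lowers it, and mild assumptions leave it near the nominal 2.5%. The range shows that the plan is sensitive to this drift; it does not estimate a bias. The remedy is cheap enough to be worth making on that basis.

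**What to change.** 1. Record the date of the qualifying stroke, and whether each analysed artery was its likely culprit, from the history and record review already done at baseline. State briefly how culprit status is assigned.
2. In D.1, pre-specify a sensitivity test of stenosis and PAV change against 0% that leaves out culprit arteries scanned soon after the stroke. A 90-day cut is one example; the documents do not support any particular value, so the sponsor should choose and justify it in advance.
3. State that a conclusion of regression should be consistent with that test.

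**Cost.** Two data items, a short rule for assigning culprit status and one extra analysis. Culprit assignment will be imprecise in some patients, and the restricted analysis will have fewer arteries and a wider interval. It should therefore be judged on the estimate as well as on significance. Enrolment and treatment are unchanged.

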
C.2.a. Secondary endpoint 1 measurement:

a) ICAD post-contrast plaque enhancement (PPE): is a dichotomous variable evaluated on the T1 pre- and post-gadolinium sequences, with multiplanar reconstruction so the ICAD can be seen in cross section.²⁶ PPE is defined by placing a region-of-interest over areas of gadolinium enhancement in ICAD to evaluate if it is equal to or exceeds the signal intensity of the pituitary infundibulum, as previously described.²⁷

- b) Carotid intraplaque hemorrhage (IPH): MPRAGE positive plaque is defined as voxels with at least 2-fold signal intensity compared to sternocleidomastoid muscle as previously described. MPRAGE positive plaques can be reliably identified. Kappa values for inter- and intra-rater reliability for detection of MPRAGE positive plaque were 0.806 and 0.818 respectively (very good agreement).^{28,29}
- c) MRA Flow Dynamics (**MFD**): We will measure MFD using accepted quantitative MRA methodology. The VERiTAS study provided prospective confirmation of the importance of MFD as a biomarker of stroke risk for patients with ICAD. Given that MFD can easily be measured in our vwMRI protocol, we will acquire the data required for its quantification.

C.3. Secondary endpoint 2

To better understand the mechanism of Repatha's effect on intra- and extracranial atherosclerosis, we will measure the endpoint of change in cholesterol markers [LDL-C, HDL-C, lipoprotein (a), apolipoprotein B, and triglyceride level]. The change in cholesterol markers will be correlated with the primary and secondary study endpoints on vwMRI. Cholesterol values will be measured at the baseline and comparison MRIs, which are 78 weeks apart. If standard of care lab values are available within 30 days of the study visit, they can be used in place of the study lab value. An additional exploratory outcome that we will measure is the composite endpoint of "recurrent stroke," which encompasses new patient-reported symptomatic ischemic stroke, transient ischemic attack, or asymptomatic strokes that emerge between MRIs.

C.3.a. Secondary endpoint 2 measurement:

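### No minimum time on the current statin dose is required before baseline, so in this single-arm study a recent statin start is counted in the LDL-C change and possibly in the pooled plaque result

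*Combined protocol and SAP*

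**What the plan says.** Two adjacent bullets in B.3.a govern lipid therapy at entry. The first reads "Current statin use or contraindication to statin". The second sets the LDL-C floor (70 mg/dL, or 60 mg/dL with lipoprotein(a) above 30 mg/dL) and requires the value to be "within a year of randomization and on the current statin medication/dose". The exclusions in B.3.b do not mention a recent statin start or dose change, and the stroke criterion gives no minimum interval since the event.

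The schedule in B.9 puts the lipid panel at screening/baseline and the first vessel wall MRI on Day 1, with no run-in. Under B.8 the drug is handed over at the baseline visit. C.3 and C.3.a allow routine laboratory values from within 30 days of a study visit to replace the study sample.

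On design and analysis, B.1 states "we propose a single arm study of Repatha in 150 patients". In C.3, secondary endpoint 2 is described thus: "we will measure the endpoint of change in cholesterol markers". D.1 compares the primary endpoints with "an assumed value of 0% change in stenosis and PAV that would correspond to optimal medical management without a PCSK9 inhibitor" and comments on statins that "some studies have suggested statin therapy can reduce carotid atherosclerosis, no such effect is known for ICAD". A separate multivariable model is "adjusted for covariates that could be confounders such as age, gender, smoking, statin use/dose and relevant medical comorbidities".

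**The concern.** A patient whose LDL-C stays above the floor on a settled statin is a different baseline from one who began the statin last week. The criteria treat them alike. For the second patient, part of the fall in LDL-C by week 78 would have happened without Repatha.

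A control arm would cancel that part. Here there is none, and all change from baseline is read as the effect of the study drug. The exposure is direct for the LDL-C change and for its planned correlation with the imaging endpoints (C.3). It is possible, but less certain, for the pooled primary analysis against 0%. The study is meant to inform a later randomised trial (A.5), so an overstated effect would carry forward into that trial's planning.

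**Working it through.** **1. What the rule fixes and what it leaves open.** The LDL-C bullet sets a maximum age for the value (one year) and an order (the draw follows the start of the current dose). It sets no minimum interval between the two. A value drawn days after starting a statin meets it.

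**2. Three separate measurements.** The qualifying LDL-C decides entry. The baseline lipid value feeds secondary endpoint 2. The Day 1 MRI feeds the primary endpoints. None has a statin-stability condition. The substitution rule is looser still: it has a 30-day window but does not require the sample to be on the current statin, so a value from before the statin began could serve as baseline.

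**3. Whether the analysis repairs it.** The covariate in D.1 is statin use and dose. A patient in the first week and one in the fifth year of the same dose have the same covariate value. The comparison with 0% is described separately, without that adjustment.

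**4. Which primary analysis is exposed.** C.1 defines two: all intra- and extracranial arteries with at least 25% stenosis, and intracranial arteries alone. D.1 concedes a possible statin effect in the carotid and says none is known for intracranial disease. On the plan's own premises, the exposure is mainly in the pooled analysis.

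**5. LDL-C arithmetic.** The plan has no figure for this, so every input here is an assumption: baseline LDL-C of 130 mg/dL in recent starters, no statin effect yet at baseline, an eventual statin effect of 30–50%, and 10–20% of patients affected.

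- Entry: a pre-statin value settles below 70 mg/dL if it is under 70/0.70 = 100 (30% effect) or 70/0.50 = 140 (50% effect).
- Statin share of one starter's fall: 130 × 0.30 = 39 mg/dL; 130 × 0.50 = 65 mg/dL.
- Overstatement of the mean fall = share of starters × statin share of the fall:

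| Share of starters | 30% effect | 50% effect |
|---|---|---|
| 10% | 3.9 mg/dL | 6.5 mg/dL |
| 20% | 7.8 mg/dL | 13 mg/dL |

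**6. Primary endpoint.** The power claim in D.2 is not affected. With one observation per patient, Φ(1 × √150 / 4 − 1.96) = Φ(1.10) = 86.5%, which agrees with the stated figure of over 80%. The issue is a shift in the mean, equal to the share of starters × the statin-driven PAV reduction in them. Neither factor is in the documents. Trial values of 10–50% and 0.25–1.0 points give shifts from 0.10 × 0.25 = 0.025 to 0.50 × 1.0 = 0.50 points, a twentyfold range that the documents cannot narrow.

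**The case against.** The case on the other side is substantial, and much of it stands.

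- **The reference value.** The plan ties 0% to optimal medical management and does not say that this management must be long established. With its statement that no statin effect is known for intracranial disease, this largely answers the concern for the intracranial analysis. It does not answer it for the extracranial arteries in the pooled analysis, or for LDL-C.
- **The LDL-C figure is near a worst case.** The qualifying and baseline values are distinct, and an early qualifying value alone does not inflate the endpoint; the baseline value must be early too. Any statin effect already present at baseline shrinks the figure. At the 50% end, 130 mg/dL settles at 65, so without raised lipoprotein(a) a stability rule would keep that patient out. The 65 mg/dL is then the distortion in the study as written, not the difference that the rule would make for that patient.
- **The endpoint is mechanistic.** The lipid predictors in D.1 are on-treatment values, which an unsettled baseline does not alter. The change score and its correlations are what is exposed.
- **Frequency.** The text permits recent starters but does not suggest that they are common.

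A reader might go further and infer that the primary result is unreliable. With about 483 effective observations (implied by the 0.51% detectable difference in D.2), the shifts in the last working step would give significant results in 5.2% to 78.4% of studies with no Repatha effect. The documents do not support that reading. It rests wholly on two invented inputs, and its upper end credits the statin with the entire 1% reduction that D.2 expects from Repatha.

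**Conclusion.** The gap is real, and nothing elsewhere in the plan closes it. Without a control arm, it lets the effect of recent statin treatment be counted in the LDL-C change and, for extracranial arteries, possibly in the pooled primary comparison with 0%. Under the assumptions shown, the mean LDL-C fall is overstated by at most about 4–13 mg/dL; with few recent starters, or with lipids already partly settled at baseline, it is less. The effect on PAV and stenosis cannot be sized from the documents, and no claim is made that it is large. The change is worth making because it is cheap and because, without the statin dates, recent starters cannot be reliably separated afterwards.

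Two wording slips in the same bullet should not be read as design faults. The window is counted from a randomisation that this study does not have, and patients with a statin contraindication have no current statin dose to which the condition can apply. The intent is clear in both cases.

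**What to change.** - In B.3.a, require an unchanged statin regimen, or a documented contraindication, for a minimum period before the qualifying LDL-C, the baseline lipids and the Day 1 MRI. The sponsor should set and justify the length; the documents give no basis for a particular figure.
- In C.3 and C.3.a, apply the same condition to any routine lipid value used in place of the baseline sample.
- Record the dates of statin start and last change. Medication history is already taken at baseline.
- In D.1, report the primary endpoints and the LDL-C change with and without patients whose statin was started or changed recently, with the cut-off fixed in advance. This is needed as well as the entry rule, because a short stability period will not remove all statin effect on plaque over 78 weeks. Splitting patients by whether they take a statin would not do: recent starters are on one.
- In the same edit, count the LDL-C window from Day 1 and state that patients with a contraindication qualify on an off-statin value.

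The cost is protocol wording, two date fields and one sensitivity analysis. The downside is a short delay for newly treated patients and a few more screen failures. The planned sample size does not change.

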All drug compliance records will be kept current and will be made available for inspection by regulatory agency inspectors. Study drug will be given to patient at the baseline visit, and preferably at 6 month intervals thereafter. Instructions for shipping study drug to patients are provided in the appendix.

B.9. Study Timeline

There are two in-person study visits (baseline and 78 week follow-up) when patients will undergo vwMRI, approximately 60 minutes long, with a simultaneous clinical evaluation by a study investigator physician and blood draw. Every 2-4 months, the study coordinator will determine medication adherence, adverse events, or patient-reported recurrent stroke (see **Figure 1**).

	Screen/ Baseline	Day 1	Day 60	Day 120	Day 180	Day 240	Day 320	Day 480	Day 546
Informed Consent	Х								
Medical History/Current medications	х		х	х	х	Х	х	х	х
Vitals	Х								Х
Review CTA or MRA ¹	х								
Vessel wall MRI		Х							Х
Pregnancy test	Х								
Creatinine	Х								Х
Lipid panel	Х								Х
Lipoprotein (a)	Х								Х
Apolipoprotein B	Х								Х
Physical exam	Х								Х
Neurological exam	Х								х
NIHSS	Х								Х
Modified Rankin Scale	х								Х
Stroke adjudication			Х	Х	Х	Х	Х	Х	Х
Adverse event determination			х	Х	х	Х	х	х	х
Serious adverse events			Х	Х	Х	Х	Х	Х	Х

Figure 1: Schedule of Activities

1. To confirm ICAD of a major intracranial artery

B.10. Study Duration

- Estimated duration of research (study start to final study deliverable): 2 Years / 6 Months
- Estimated duration of first patient enrolled to last patient out: 2 Year / 0 Months
- Estimated duration for Amgen to supply study drug: 2 Year / 0 Months

C. Study Endpoints

C.1. Primary Endpoints

The primary endpoints are nominal change in the stenosis and percent atheroma volume (PAV) of cerebrovasculture arteries from baseline to week 78. We will use measure stenosis and PAV on vessel wall MRI (vwMRI), which evaluates all arteries from the aortic arch to the distal intracranial vasculature in a single scan. The primary endpoints will be analyzed for both: 1) all intra- or extracranial arteries that have at least 25% stenosis, and 2) seperately for the intracranial arteries. Stenosis and PAV will be measured using standard methodology.

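### Entry criteria exclude PCSK9 inhibitor allergy but not current or recent use, so some patients could start from an already treated baseline and dilute the single-arm change toward zero

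*Combined protocol and SAP*

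**What the plan says.** All entry criteria are in B.3.a and B.3.b. The only one that mentions the drug class is "Gadolinium or PCSK9 inhibitor allergy". The other exclusions concern kidney function, MRI contraindications, ability to return and pregnancy. Background lipid therapy appears only as "Current statin use or contraindication to statin".

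The lipid criterion is "Fasting LDL-C ≥ 70 mg/dL or LDL-C ≥ 60 mg/dL if lipoprotein (a) > 30 mg/dL", and the value must be "within a year of randomization and on the current statin medication/dose". It is tied to the statin and to no other lipid-lowering drug.

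The schedule of activities (B.9, Figure 1) collects "Medical History/Current medications" and a lipid panel at screening. No entry rule uses the medication list to deal with PCSK9 inhibitors.

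Under B.2, patients "will have an MRI before beginning study medication". That fixes the scan relative to the trial's supply of drug, not relative to any earlier use of the class. In C.1, "The primary endpoints are nominal change in the stenosis and percent atheroma volume (PAV) of cerebrovasculture arteries from baseline to week 78". D.1 compares that change with an assumed 0%, a value "that would correspond to optimal medical management without a PCSK9 inhibitor".

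**The concern.** The study has one arm. Its main inference is that change from baseline, set against 0%, reflects the addition of a PCSK9 inhibitor. That requires a baseline free of the class, and the entry criteria do not secure one.

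Two kinds of patient meet every criterion as written:

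- one who started a PCSK9 inhibitor after the qualifying LDL-C test, with statin and dose unchanged;
- one who is on a PCSK9 inhibitor and still has LDL-C at or above the floor.

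Such patients are plausible, because B.4 states that the study population already falls within the approved indication and so could receive the drug in ordinary care. Part or all of their plaque response may precede the baseline scan. There is no control arm in which the same patients would appear, and the adjustment covariates named in D.1 include statin use and dose but not earlier PCSK9 inhibitor use. At stake is an effect estimate pulled toward zero in a study whose stated purpose (A.5) is to inform the design of a later randomized trial.

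**Working it through.** **Inputs from D.2.** 150 patients; four PAV sites per patient; 1% reduction against 0%; SD 4%; two-sided alpha 0.05; withdrawal 25–30%. At 30% withdrawal, 150 × 0.70 = 105 patients complete. The ICC is not given, so it is varied. D.2 gives no effect size or SD for stenosis, so the arithmetic covers PAV only.

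**Formulas** (one-sample normal approximation):

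- Effective sample size: N_eff = n × m / (1 + (m − 1) × ICC)
- Power = Φ(δ × √N_eff / SD − 1.96)

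**The plan's own figures first.**

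- One measurement per patient (equivalent to ICC = 1): N_eff = 150, so Φ(√150/4 − 1.96) = Φ(1.10) = 86.5%. Four sites at any lower ICC give more, so the stated power above 80% reproduces.
- The 0.51% minimum detectable effect needs N_eff = ((1.96 + 0.84) × 4 / 0.51)² ≈ 483. That implies ICC = (600/483 − 1)/3 ≈ 0.08. This value is used below as the ICC implied by the plan.

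**Dilution.** Let f be the share of patients already treated at baseline and d their further PAV reduction, with d between 0 and 1%. The mean reduction is (1 − f) × 1% + f × d. It is smallest at d = 0, where it equals (1 − f)%. Neither f nor d is in the documents. The values below are assumptions, and d = 0 gives the most dilution unless prior users progress.

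| f (assumed) | Mean PAV reduction | Power, 105 completers, 4 sites, ICC 0.08 | Power, 105 completers, 4 sites, ICC 0.3 |
|---|---|---|---|
| 0 | 1.00% | 99.6% | 96.1% |
| 5% | 0.95% | 99.2% | 94.2% |
| 10% | 0.90% | 98.5% | 91.7% |
| 20% | 0.80% | 95.7% | 84.5% |

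Worked entry for f = 10%, ICC 0.3: N_eff = 105 × 4 / (1 + 3 × 0.3) = 420/1.9 = 221.1. Power = Φ(0.90 × √221.1/4 − 1.96) = Φ(3.345 − 1.96) = Φ(1.385) = 91.7%.

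For contrast, with one measurement per patient and all 150 patients, power falls from 86.5% to 78.7% at f = 10%. That is not the planned design.

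**The case against.** The strongest reply is that few such patients would enter. The background section says the class lowers LDL dramatically, so a patient on treatment when tested would often miss the floor. Anyone who slipped through would be visible on the screening medication list and could be handled in a sensitivity analysis. In the start-after-the-test route, exposure before baseline is at most about a year, against 78 weeks of study treatment, so nothing shows that the response would be used up. The bias also works against the study's hypothesis and would not create a false positive. All of this stands, and it limits the size of the point. It does not close the gap: collecting a medication list is not an entry rule, and no sensitivity analysis for prior users is written.

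A reader might infer more than the documents support:

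- **That the year-old LDL-C enters the change score.** It does not. C.3 and C.3.a take the lipids at the study MRIs, or from routine results within 30 days. The old value affects eligibility only.
- **That starting any other lipid-lowering drug causes the same problem.** The comparator in D.1 is management without a PCSK9 inhibitor, and other agents are compatible with that. A recent change in them would be a different issue, confounding, which could push the estimate the other way.
- **That the LDL-C relation is biased toward null throughout.** C.3 correlates change in lipids with change in imaging. A prior user with little of both need not flatten that line. Attenuation is arguable only for the on-treatment LDL-C model in D.1.
- **That the LDL-C floor was meant to exclude users and failed.** The documents state no such purpose.

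**Conclusion.** The point holds as a gap in eligibility. A current or recent PCSK9 inhibitor user can meet every written criterion, and the primary comparison presumes a baseline free of the class. The consequence is dilution of the estimated effect toward zero.

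Its size is unknown and may be small. Under the assumption of no further change in prior users, each 10% of such patients removes at most 0.10 percentage points from the planned 1% PAV effect. The loss of power under the four-site design is modest: at f = 10%, from 99.6% to 98.5% at ICC 0.08, or from 96.1% to 91.7% at ICC 0.3, with 105 completers. The documents do not support a conclusion that the trial becomes underpowered; that would need a much larger share of prior users, a much higher ICC, or a single measurement per patient. This is a cheap improvement, worth making mainly to keep the effect estimate and the baseline lipids interpretable.

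**What to change.** Add to B.3.b an exclusion for current or recent PCSK9 inhibitor use, with a look-back period defined by the sponsor and checked against the medication list already collected at screening. In B.3.a, require that no PCSK9 inhibitor was started after the qualifying LDL-C. While editing that line, replace its reference to randomization, which a single-arm study does not have, with a defined date such as enrollment.

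The cost is a few lines of protocol wording and a slightly smaller eligible pool. No new data collection is needed.
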